### **9.3.5 Adverse Event Reporting**

All reporting is done in accordance with StrokeNet SOPs for Safety Monitoring and Reporting as outlined in the administrative documents available on the website. Clinical sites will be responsible for submitting event reports in WebDCU and responding to queries for additional information in a timely manner. The MPIs will be responsible for ensuring that AE data is assessed and recorded appropriately following GCP guidelines.

### **9.3.6 Notifying Regulatory Authorities, Investigators, and Institutional Review Board**

The SISTER MPIs will inform Investigators, IRB/ECs, and regulatory authorities of any Suspected Unexpected Serious Adverse Reactions (SUSARs) occurring in other study sites or related to other studies of the investigational drug, as appropriate per local reporting requirements.

In the U.S., upon receipt of the Sponsor's notification of SUSARs that occurred with the study drug, unless delegated to the Sponsor, it is the Investigator's responsibility to inform the IRB per Sponsor's instruction.

---

### **9.3.7 Adverse Events of Special Interest**

Adverse Events of Special Interest should always be reported to the Sponsor as soon as possible following the procedures outlined in Section 9.3.5 for Adverse Event reporting, with the Investigator's assessment of seriousness, causality, and a detailed narrative.

These include:

- Combined elevations of aminotransferases and bilirubin, either serious or nonserious and whether or not causally related, meeting the criteria of a potential Hy's Law case (total bilirubin level  $\geq 2 \times$  upper limit of normal (ULN) with simultaneously ALT or AST  $\geq 3 \times$  ULN).
- Symptomatic ICH as defined above.

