## **Special Populations**

TS23 has not yet been tested in children, adults over 60 years of age, or participants with renal or hepatic impairment.

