## 8.1 Baseline

Patients presenting with acute ischemic stroke will be evaluated by a stroke team physician, in accordance with institutional practice, to establish study eligibility. All consecutive patients meeting study entry criteria will be enrolled in the trial.

Participants enrolled in SISTER should not receive antithrombotics for at least 24 hours after study drug administration.

The study order sets will specifically include an order not to administer antithrombotics within the first 24 hours after study drug administration. This will also be closely monitored as participants will be admitted to the intensive care unit setting for at least first 24 hours after drug admission.

The following data will be documented at the baseline evaluation for randomized patients:

- Demographics: Age, sex, race/ethnicity
  - Medical history regarding presence of concomitant medical conditions (e.g. hypertension, diabetes, hyperlipidemia, atrial fibrillation, prior ischemic stroke, prior hemorrhagic stroke, current or past smoking)
  - Vital signs: Systolic and diastolic arterial blood pressure; heart rate, temperature
  - Concomitant medications at time of stroke onset (anticoagulation, antiplatelets, antihypertensives, statins, antidiabetics, cholesterol reducers)
  - Pre-stroke functional state: pre-stroke modified Rankin Scale, pre-stroke ambulatory status (independent, with assistance, unable)
  - Laboratory Evaluation
    - Measurement within 12 hours prior to study drug administration (if there are multiple measurements, then consider the latest measurement)
      - SOC: aPTT, PT with INR, CBC, platelet count.
    - First measurements upon presentation to study hospital, within 2-3 hours of study drug administration):
      - SOC: Glucose, creatinine
    - First value collected during hospitalization:
      - SOC: Hemoglobin A1C, Lipid Panel containing total cholesterol, HDL, LDL & triglyceride.
  - Neurologic Deficit: NIHSS upon arrival to the study hospital
-

- Brain and Vascular imaging at presentation:
    - CT or MRI
    - CTA or MR angiography (MRA)
    - CTP or MRI-PWI, if applicable per institutional practices
  - Initial Workflow Time Metrics: Date and time of:
    - Last known well (LKW)
    - Symptoms first observed (SFO)
    - Outside hospital (OSH) date/times (if patient first presented to an OSH):
      - Arrival at OSH (“Door-In”)
      - Departure from OSH (“Door-Out”)
    - Study Hospital date/times:
      - Arrival at Study Hospital

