## 8.2 Pre-Randomization/Randomization visit

- Time of randomization
- Time of study drug administration
- Time of study drug completion
- Baseline research related laboratory studies (prior to study drug administration):
  - Fibrinogen – processed and resulted at site.
  - a2AP, MMP-9 levels and PK studies – processed and frozen. This will be shipped to the central laboratory

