## 8.3 3 ( $\pm 1$ ) Hours Post Study Drug Administration

- Research labs:
  - Fibrinogen - processed and resulted at site.
  - a2AP, and MMP-9 levels and PK studies - processed and frozen. This will be shipped to the central laboratory

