## 8.4 30 ( $\pm 4$ ) Hours Post Study Drug Administration

- Research related labs:
    - Fibrinogen, PT/INR, aPTT to be processed and resulted at site
    - a2AP, and MMP-9 levels and PK studies to be processed and frozen. This will be shipped to the central laboratory
  - SOC Labs:
    - CBC
-

- NIHSS assessed by blinded, certified rater
  - Basic metabolic panel (glucose, calcium, sodium, potassium, carbon dioxide, and chloride, BUN creatinine) at 30 ( $\pm 4$ ) hours post study drug administration if done as standard of care
  - Vital Signs
  - Non contrast CT Brain (reading will be performed centrally) (**Please note that an MRI cannot substitute for the CT**)
    - ASPECTS score
    - Any radiologic hemorrhage (further classified as SAH, HI1, HI2, PH1, PH2, RIH, IVH, SDH, EDH) on CT
  - CTA or MRA head (required only if visible vessel occlusion present on the baseline CTA or MRA per site read).
    - Presence of a visible vessel occlusion
    - Location of vessel occlusion (per the central reader): ICA, M1 MCA, M2 MCA, M3/M4 MCA, A1 ACA, A2-5 ACA, VA, BA, P1 PCA, P2 PCA, P3/4 PCA, PICA, AICA, SCA, Other
  - CT/MR perfusion
    - Perfusion lesion volume (volumes of regions with  $T_{\max} > 6$  sec and  $> 10$  sec on CTP or PWI MR)
    - Ischemic core lesion volume (on CTP -volume of region with  $rCBF < 30\%$ ; on DWI-volume of region with  $ADC < 620 \times 10^{-3}$  mm/s)
    - If the participant underwent CT perfusion at baseline, then CT perfusion should be obtained at 30 ( $\pm 4$ ) hours.
    - If the participant underwent MR perfusion at baseline, then MR perfusion should be obtained at 30 ( $\pm 4$ ) hours.
  - Symptomatic intracranial hemorrhage [symptomatic ICH, as per SITS-MOST definition (a local or remote type II parenchymal hemorrhage within 30 ( $\pm 4$ ) h after treatment associated with a  $\geq 4$ -point deterioration on the NIHSS score from baseline or from the lowest score from baseline to 24 hours, or leading to death.)] ([Wahlgren, Ahmed et al. 2007](#))
  - Major non-ICH systemic hemorrhage
  - Clinically relevant systemic hemorrhage
-

- AE
- SAE
- UPs

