### 8.8 Day 90 ( $\pm 7$ ) Visit

- mRS
- NIHSS
- Concomitant meds
- Laboratory studies
  - Pharmacokinetic profile of TS23 and evaluation of anti-drug antibodies to TS23 at 90 ( $\pm 7$ ) days. Specimens are processed and frozen at site for every 6-month batch shipping to core lab.
  - (CBC, CMP, and Lipid profile if collected as standard of care at 90 ( $\pm 7$ ) days).
- AEs, SAEs, and UPs

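### Potential Hy's Law cases are an adverse event of special interest, but no visit requires ALT, AST or bilirubin, so cases surface only opportunistically and a zero count needs the number tested

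*Protocol*

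**What the plan says.** Protocol section 9.3.7 names two AESIs that sites must report promptly with an assessment of seriousness and causality and a narrative. One is symptomatic ICH. The other is the potential Hy's Law case: "Combined elevations of aminotransferases and bilirubin, either serious or nonserious and whether or not causally related", with thresholds of 2 times the upper limit of normal for total bilirubin and, at the same time, 3 times for ALT or AST.

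The laboratory tests are itemised by visit in section 8:

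- Baseline (8.1): "SOC: aPTT, PT with INR, CBC, platelet count"; then "SOC: Glucose, creatinine"; then HbA1c and a lipid panel.
- Before dosing (8.2), under "Baseline research related laboratory studies (prior to study drug administration"): fibrinogen, a2AP, MMP-9 and PK.
- 3 h (8.3): fibrinogen, and "a2AP, and MMP-9 levels and PK studies - processed and frozen".
- 30 h (8.4): fibrinogen, PT/INR, aPTT, a2AP, MMP-9, PK and CBC. In addition "Basic metabolic panel (glucose, calcium, sodium, potassium, carbon dioxide, and chloride, BUN creatinine"), but only where routine care includes it.
- Day 90 (8.8): PK and anti-drug antibodies, and "CBC, CMP, and Lipid profile if collected as standard of care at 90" days.

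Sections 8.5 (72 h), 8.6 (discharge) and 8.7 (day 30) list no laboratory tests. On earlier experience, section 6.1.1 (Special Populations) says: "TS23 has not yet been tested in children, adults over 60 years of age, or participants with renal or hepatic impairment".

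**The concern.** An event defined only by laboratory values exists in the data only if someone measures those values. Here the protocol asks for prompt reporting of a combined bilirubin and aminotransferase elevation but does not ask any site to measure bilirubin, ALT or AST. A site that follows the protocol exactly need never generate the data that would trigger the report.

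Two things follow. First, there is no pre-dose reference. Section 9.3.4 treats a condition present at screening as baseline, to be recorded as an adverse event only if it worsens, and section 9.3.3.2 asks whether the participant's clinical state explains the event. For a liver abnormality that nobody knew about, neither question can be answered without a value from before the infusion. Second, there is no denominator. If the final report says that no potential Hy's Law case occurred, the reader cannot tell whether 300 participants were tested or very few, or whether testing differed between arms.

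**Working it through.** The protocol gives no expected rate, testing rate or count for this event, so there is no figure to reproduce. The check is whether the definition and the visit lists fit together.

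**Step 1: what the definition needs.** Total bilirubin, plus ALT or AST, measured at the same time (section 9.3.7).

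**Step 2: what each visit supplies.**

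| Visit | Required ALT, AST or bilirubin | Optional source in the list |
|---|---|---|
| Baseline and pre-dose (8.1, 8.2) | none | none |
| 3 h (8.3) | none | none |
| 30 h (8.4) | none | none: the eight analytes of the optional basic panel include no liver test |
| 72 h (8.5) | none | none |
| Discharge (8.6) | none | none |
| Day 30 (8.7) | none | none |
| Day 90 (8.8) | none | CMP, if routine care includes it |

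The Schedule of Activities (1.3) adds nothing: its footnotes name PK/PD, fibrinogen, PT/INR, aPTT and CBC. The protocol's abbreviation list does not define CMP. I assume a comprehensive metabolic panel, which ordinarily includes the three analytes. Required measurements are therefore 0 at every visit, and the single optional source falls about three months after one infusion of about 15 minutes.

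**Step 3: compare with the other AESI.** Symptomatic ICH is supported by a required CT and a required NIHSS at 30 h (1.3 and 8.4). Only the hepatic AESI has no scheduled measurement behind it.

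**Step 4: what a zero count could mean.** With 0 events among n participants tested, the exact one-sided 95% upper limit for the true rate is 1 − 0.05^(1/n). The chance of seeing at least one case at true rate p is 1 − (1 − p)^n. The planned sample size is 300 (section 4.1). The fraction tested is not in the protocol, so the fractions below are assumptions shown as a range.

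| Fraction tested (assumed) | n | Upper limit if 0 cases | Chance of at least 1 case if p = 1% |
|---|---|---|---|
| 100% | 300 | 0.99% | 95% |
| 50% | 150 | 2.0% | 78% |
| 25% | 75 | 3.9% | 53% |
| 10% | 30 | 9.5% | 26% |
| 5% | 15 | 18.1% | 14% |

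For example, with n = 30: 1 − 0.05^(1/30) = 0.095, and 1 − 0.99^30 = 0.26. These pool the arms; within one arm the limits would be wider.

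**The case against.** The strongest reply is that section 9.3.7 sets a reporting duty, not a derived endpoint. Section 9.3.1 lets investigators judge abnormal laboratory findings to be adverse events. Section 9.3.4 lets events come to light at visits, when a participant seeks care, or on monitor review. Section 8.8 records a day-90 panel where one was done. So a case can be found and reported. That stands, and a reader should not infer that the event cannot be derived at all. The documents support only that it is not ascertained systematically.

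Nor is liver injury a primary or secondary endpoint, and it does not enter the utility function, the safety stopping rule or the success criterion. The protocol promises no Hy's Law rate. A reader might infer that a zero count would be worthless; the accurate statement is that it cannot be interpreted without the number tested.

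It can also be said that the documents report no hepatic signal. Phase 1 included chemistry and found no clinically relevant laboratory trends (section 2.4), and TS23 is given once. That makes opportunistic capture a defensible choice, provided the protocol says so. It rests on four cohorts of six healthy volunteers, and section 2.5.1 acknowledges that unknown side effects are possible.

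Finally, one might read the Special Populations statement with section 5.2, which has no hepatic criterion, as showing that an exclusion is missing. It does not: the statement describes prior experience and sets no eligibility rule. Known liver disease can also be recorded in the open list of medical conditions at baseline. What goes unseen is the unrecognised abnormality.

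**Conclusion.** The point holds in a limited form. Section 9.3.7 names a laboratory-defined AESI, and the Schedule of Activities and sections 8.1 to 8.8 require none of the three analytes at any visit. Detection is opportunistic, there is no required pre-dose reference value, and any count lacks a denominator. How much a zero count would show depends on an unknown number: the upper limit runs from 0.99% with all 300 tested to 18.1% with 15 tested, where the tested fractions are my assumptions.

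This weakens one safety statement and leaves the primary analysis untouched. It is worth correcting because the present text suggests monitoring that the schedule does not deliver. The SAP, which is not at hand, could define how cases are counted, but it cannot supply measurements that were never taken.

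**What to change.** Reconcile section 9.3.7 with sections 1.3 and 8. Add ALT, AST and total bilirubin as required tests, resulted at the site, at the existing blood draws: pre-dose (8.1/8.2), 30 h (8.4) and day 90 (8.8). The pre-dose value would serve as a reference only; no change to eligibility is proposed.

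The tests must be required in their own right. Replacing the 30 h basic panel with a comprehensive one would not close the gap, because that panel is done only when routine care includes it.

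The cost is small: three routine analytes, with no new visit or venipuncture. The downsides are a modest laboratory cost, some incidental abnormal values to follow up, and an extra site step at day 90, where research specimens are currently frozen for batch shipping. Cases arising between 30 h and day 90 would still depend on routine care.

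If the tests are not added, either delete the Hy's Law AESI, or state in 9.3.7 that it is captured only from routine care and report the number tested per arm beside any count. The latter needs a field recording whether liver tests were done, and when.

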### **9.3.8 Reporting of Pregnancy**

The MPIs must be notified of any subject who becomes pregnant while receiving study medication after the last dose of study medication. If a female subject partner becomes pregnant within 7 days after the subject receives study medication, the pregnant female partner will be consented so that the pregnancy can be followed through 7 days after birth of the infant.

Although pregnancy is not technically an AE, all pregnancies must be followed to conclusion, 7 days after birth, to determine their outcome. This information is important for both drug safety and public health concerns. It is the responsibility of the Investigator, or designee, to report any pregnancy in a female subject or female partners of male participants using the Exposure In Utero (EIU) Reporting form. Please contact your StrokeNet National Coordinating Center Project Manager to receive the EIU Reporting Form upon learning of a pregnancy. The Investigator should make every effort to follow the subject until completion of the pregnancy and complete the EIU Reporting Form with complete pregnancy outcome information, including normal delivery and induced abortion. The adverse pregnancy outcome, either serious or non-serious, should be reported in accordance with study procedures. In case of pregnancy in the female partner of a male patient, the outcome of the pregnancy should be obtained if the female partner agrees. If the outcome of the pregnancy meets the criteria for immediate classification as an SAE (i.e., post-partum complications, spontaneous or induced abortion, stillbirth, neonatal death, or congenital anomaly, including that in an aborted fetus), the Investigator should follow the procedures for reporting SAEs outlined in Section 9.3.5.

## **9.4 Unanticipated Problems**

### **9.4.1 Definition of Unanticipated Problems (UPs)**

The Office for Human Research Protections (OHRP) considers UPs involving risks to participants or others to include, in general, any incident, experience, or outcome that meets **all** of the following criteria:

Unexpected in terms of nature, severity, or frequency given (a) the research procedures that are described in the protocol-related documents, such as the IRB-approved research protocol and informed consent document; and (b) the characteristics of the participant population being studied;

Related or possibly related to participation in the research (“possibly related” means there is a reasonable possibility that the incident, experience, or outcome may have been caused by the procedures involved in the research); and

Suggests that the research places participants or others at a greater risk of harm (including physical, psychological, economic, or social harm) than was previously known or recognized.

This definition could include any serious adverse effect on health or safety or any life-threatening problem or death caused by, or associated with, the drug, if that effect, problem, or death was not previously identified in nature, severity, or degree of incidence in the investigational plan or application (including a supplementary plan or application), or any other unanticipated serious problem associated with the drug that relates to the rights, safety, or welfare of participants (21 CFR 812.3(s)).

#### **9.4.2 Unanticipated Problem Reporting**

The investigator will report UPs to the reviewing IRB/EC and to the NCC/NDMC. The UP report will include the following information:

- Protocol identifying information: protocol title and number, PI’s name, and the IRB project number;
- A detailed description of the event, incident, experience, or outcome;
- An explanation of the basis for determining that the event, incident, experience, or outcome represents an UP;
- A description of any changes to the protocol or other corrective actions that have been taken or are proposed in response to the UP.

An investigator will be required to submit to the sponsor and to the reviewing IRB/EC a report of any UPs occurring during an investigation as soon as possible, but in no event later than 10 working days, after the investigator first learns of the effect.

#### **9.4.3 Emergency Contact**

All investigators will have access to a 24-hour study hotline, staffed by SISTER PIs, in case of emergency questions. The study PIs and project managers will be available via email for non-emergent study questions.

### **9.5 Interim Monitoring of Events**

The Independent Medical Monitor (IMM), who is independent from any involvement with the study, will monitor the study with regard to safety on an ongoing basis to identify any safety concerns. The

---

IMM also will review all SAEs and determine whether they are related to study intervention (as described above) and will communicate with the investigators for any questions or clarifications regarding an event. Periodically throughout the study, the Executive Committee and the IMM will review reports on the incidence rates of all reported AEs, whether serious or not. Should such monitoring uncover issues that may threaten subject safety (e.g., unexpectedly high rate of AEs), the study statistician and PIs will prepare a report to be submitted to the DSMB for their review proposing further actions to be taken, if any. In addition to monthly Safety Reports, a comprehensive DSMB reports will be generated semi-annually by the NDMC: an open report to be distributed to the Executive Committee and IMM, and a closed report to be distributed only to the DSMB. Each semi-annual report will provide cumulative summary statistics on enrollment, subject status in the study, baseline characteristics, protocol violations, safety data (including a summary of the most frequent and most serious AEs, a summary of all MedWatch Reports, and a listing of all participants who were terminated from the study and the reason for termination), and data management/quality information. The open report statistics will be provided for the overall study with no separation of treatment groups. The closed report will provide cumulative summary statistics by partially blinded treatment group to DSMB members, the NIH liaison, and the project's unblinded statistician. All people with access to the closed reports will be fully independent from trial operation, and have no impact on patient recruitment, treatment, and assessment. If the DSMB wishes to be completely unblinded for these reports, a sealed identification envelope will be provided to the DSMB liaison; this envelope can be opened at the discretion of the DSMB. An annual report will be submitted to the FDA.

## 10 STATISTICAL CONSIDERATIONS

### 10.1 General Approach

This study is Phase IIa, Bayesian, adaptive, dose-finding trial. This study was designed and all simulations were performed using the Fixed and Adaptive Clinical Trial Simulator FACTS™ v6.4 Core Design software developed by Berry Consultants.

### 10.2 Primary Analysis

The primary analysis will be Bayesian. We will test whether the best dose of TS23 has at least 25% Utility ("Promising Zone"). The trial is a success if the best dose has utility of 0.25 or higher with at least 80% probability. Such a utility can be achieved through various combinations of 24-hour NIHSS improvement and ICH rate.

#### 10.2.1 Dose-Response Models

For each endpoint, we model the dose-response relationship using a Bayesian, normal dynamic linear model (NDLM). This type of model is appropriate for a variety of dose-response shapes including non-monotonic. The NDLM is a method of smoothing between neighboring groups and was proposed for dose-finding trials by Berry in 2002. Both NDLM models assume weakly informative priors (for baseline NIHSS and control group) or non-informative priors (for smoothing parameters). The model details are provided in the SAP.

